1.1.3 Exploratory Aims

The exploratory aims of this trial include measuring clinical changes for possible inclusion in the future trial.

- 1) To determine if MTM in Stage 2 improves the subject's nutritional intake by measuring the proportion of subjects who meet protein intake goals (1g/kg/day) and caloric intake goals (30c/kg/day) as assessed using the 24-Hour Diet Recall and/or VioScreen FFQ from baseline to 9 weeks.
- 2) To determine whether MTM in Stage 2 improves reported cognitive function.
 - Comparison of Encephalapp Stroop scores from baseline to 11±2 weeks. We aim to evaluate whether there is normalization in individual scores, by comparing the proportion of subjects with a 'normal' score at baseline to 11±2 weeks, with a score of < 190 seconds defined as normal.
 - Comparison of Animal Naming Test (ANT) scores from baseline to 11±2 weeks and 24±3 weeks. We aim to evaluate whether there is normalization in scores, by comparing the proportion of subjects with a 'normal' score at baseline to 11±2 weeks and 24±3 weeks, with a score of >10 animals defined as normal.
- 3) To determine if MTM in Stage 2 improves self-reported HRQOL.
 - Comparison of Short Form-8 Health Survey (SF-8) score from baseline to 11±2 weeks and 24±3 weeks. We aim to determine the proportion of subjects who experience $\geq 5\%$ improvement in SF-8 score from baseline to 11±2 weeks and 24±3 weeks.
- 4) We will explore patient satisfaction and preferences of MTM with a qualitative assessment conducted at the final study visit conducted via phone at 24±3 weeks.
- 5) We will explore if MTM in Stage 2 improves health outcomes and healthcare utilization rates including:
 - Healthcare Utilization: We will compare number of reported total hospital days, number of Emergency Room (ER) visits, number of paracenteses, number of all-cause hospitalizations, number of hospitalizations due to overt HE and number of subjects who undergo liver transplantation or die at different time points throughout the study, ranging from 90 days prior to enrollment to 24±3 weeks.
 - Clinical Outcomes: Comparison of MELD-Na score, serum albumin concentration, diuretic dose, weight, and HE therapies at different time points throughout the study, ranging from 90 days prior to enrollment to 24±3 weeks.

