2. STUDY DESIGN

Overview: We propose a two-stage trial to determine the feasibility of MTM intervention in cirrhosis patients with a history of HE. Stage 1 will assess the feasibility of 10 different assessments and 2 weeks of MTM among three different cirrhosis populations, 1) patients with a history of \geq Grade 2 HE, 2) patients with a history of moderate to severe ascites and 3) patients with compensated cirrhosis to determine if any of the feasibility concerns are specific to particular cirrhosis complications. Patients from each group will be enrolled in equal proportion with a total of at least 30 subjects. Baseline assessments will be conducted in person at baseline and at the final study visit after completion of 2 weeks MTM intervention at 4 ± 1 weeks.

Figure 1. Stage 1 Study Design

Stage 2 is a pre-post trial after refining selection of assessments based on subject ability to complete procedures and detect changes in outcomes of Stage 1. We will enroll at least 20 subjects with a history of \geq Grade 2 HE. This stage begins with a 4 ± 1 week run-in phase with patients enrolled in person or via phone. Patients are observed in this run-in period to demonstrate interest in completing the study. Subjects will return to the clinic for a study visit in order to complete baseline assessments. Subjects in Stage 2 subjects will receive 6 weeks of MTM. During the intervention phase, subjects will receive weekly phone calls and will also be required to complete dietary recall assessments in order to measure whether they are consuming the MTM. After completion of MTM intervention, subjects will return to the clinic for an in person visit where they will repeat all baseline assessments. Thereafter, there is a 12-week observational period. Subjects will complete their final study visit and exit interview via phone between Weeks 21 and 27; Study Days 150 – 194 (SD 172 \pm 22) in order to complete final assessments.

Figure 2. Stage 2 Study Design

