Food recalls are a common and accurate method of assessing dietary intake in adults. All foods and beverages consumed within the past 24-hours will be recorded using the USDA 5-pass method built into the Nutrition Data System for Research (NDSR) program. Nutrition Assessment Laboratory (NAL) dietitians have been trained and standardized to complete dietary recalls. Specific forms may be utilized to assist participants in the estimation of portion size. In order to reduce error, quality control measures are both built into the NDSR program and are employed after data collection is complete by NAL management. NDSR data output provides a series of files to allow nutrient analysis per ingredient, food, meal, and day. Food group serving count information for 168 food subgroups is also provided per food, meal, and day. The 24-hour dietary recall will be conducted by NAL dieticians at the University of Michigan Nutrition Obesity Research Center via phone.

11. Exit Interview (Appendix F)

An 11-item questionnaire containing multiple choice and open-ended questions to assess the subjects preferences and satisfaction with MTM and the nutrition education handout.

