4.3.2 Intervention

After baseline assessments are complete, the following steps to implement the MTM intervention with subjects will occur in clinic:

1. All subjects will receive Standard of Care (SOC), which is a standardized nutrition education handout containing instructions on following a high-protein+sodium restricted diet (depending on the presence of ascites).
2. All subjects will enroll in MTM designed and prepared by PurFoods, LLC (Des Moines, IA). PurFoods specializes in providing home-delivered, specialized dietitian-curated meals to patients with various medical conditions such as liver disease, chronic kidney disease, cancer and cardiovascular disease. Additional information about the company and their services can be found here: <https://www.momsmeals.com/>. Subjects will receive meals that adhere to their specified nutritional targets dependent upon their cirrhosis complication of hepatic encephalopathy and/or ascites. Subjects with HE will

receive high-protein (approx. 1g/kg/day) and high-calorie (approx. 30c/kg/day) meals. Subjects with HE and ascites will receive high-protein and high-calorie meals that are also low-sodium (<2000g/day). The study coordinator will place an order with PurFoods for each subject after their baseline assessments are complete. Subjects will select from an available menu of meal options each week that adhere to the specified nutritional targets as above. A staff member from PurFoods will contact the subject via phone or email to complete meal selection. Study food will be pre-packaged for storage with preparation (typically microwave heating) to be completed at home by the subject and will be delivered every 1 to 2 weeks under the direction of PurFoods.

3. In addition to home-delivered meals, the study coordinator will provide each subject with a daytime and nighttime protein supplement (approx. 15g protein) to be consumed daily at home during the same study days as MTM. The daytime protein supplement is a protein bar (ZonePerfect or Perfect Bar). The protein supplements will be provided to subjects in person after baseline completion or the study coordinator will ship them to the subject's home if in remote operations.

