4.3.3 Follow-Up & Outcomes

The first end point for Stage 2 is at the end of the MTM intervention. All subjects should complete the MTM intervention between Week 9 and 11; Study Days 66 and 82 (SD 74±8), barring any hospitalizations or other complications that may delay completion (see sections 4.4 and 4.5 below). The subjects will return for a second in-person visit within 2 weeks of completing intervention, between Weeks 9 and 13 (11±2 weeks); Study Days 66 and 96 (SD 81±15). At this visit, all baseline assessments will be repeated with the subject in the same order identified above (section 4.3.1). If we are conducting study procedures remotely, this visit will be conducted via phone. The EncephalApp Stroop and Liver Frailty Index will not be conducted in this circumstance. All subjects will be asked to complete the VioScreen FFQ at home within 2 weeks of completing the intervention (Weeks 9 and 13 (11±2 weeks); Study Days 66 and 96 (SD 81±15)).

Patients will then be observed for an additional 12 weeks from the date of second in-person visit. Subjects will be contacted biweekly via phone and/or email during this period to maintain contact. The main purpose of the phone calls during this time period is to maintain communication with the subject in order to prevent lost to follow-up. However, the study coordinator will also ask the subject to report their current weight. The observation period will be concluded with a phone assessment about healthcare utilization, an exit interview regarding their preferences and satisfaction with MTM (Appendix F), and the subject will also complete the ANT and SF-8. The final phone assessment represents the final end point of Stage 2 and will occur between Weeks 21 and 27 (24±3 weeks); Study Days 150 – 194 (SD 172±22).

The primary outcomes of Stage 2 are the subject retention rate at 24±3 weeks post-enrollment and the MTM intervention adherence rate at 9±2 weeks post-enrollment. Secondary outcomes measured at 24±3 weeks post-enrollment include proportion of subjects who complete all assessments and procedures, HRQOL (SF-8), cognitive function (ANT) and healthcare utilization rates and clinical outcomes. Other secondary outcomes include the proportion of subjects who complete all 24-hour Diet Recall interviews, the proportion of subjects who report improved nutritional intake and cognitive function assessed by the Encephalapp Stroop.

Table 2. Stage 2 Procedure Table

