6. STATISTICAL CONSIDERATIONS

6.1 SAMPLE SIZE AND ACCRUAL

The sample size for this feasibility study not driven by any hypothesis test but reflects clinical judgement. For stage 1, our prior experience suggests that 10 patients per condition is enough to detect major study barriers. For stage 2, we hope but have no way of knowing whether the intervention will impact the outcomes given its novelty. It is for that reason that we are conducting a pilot with a reasonable number of patients where outliers would not drive results.

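### Stage 2 dietary intake is reported only as a goal count, which is less sensitive than the paired mean change and lets separately supplied supplement protein count towards the protein goal

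*Combined protocol and SAP*

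**What the plan says.** Section 1.1.3, item 1, asks whether medically tailored meals improve intake in Stage 2. It answers by "measuring the proportion of subjects who meet protein intake goals (1g/kg/day) and caloric intake goals (30c/kg/day"). The instrument and the period are then given: "as assessed using the 24-Hour Diet Recall and/or VioScreen FFQ from baseline to 9 weeks". It does not say whether the two goals are to be met jointly or counted separately.

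Section 4.3.3 lists intake among the secondary outcomes, as "the proportion of subjects who report improved nutritional intake", with no threshold. The summary table and section 1.1.3 place intake among the exploratory outcomes. The Stage 2 endpoint list in section 1.2 omits it.

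Sections 4.3.1 and 4.3.2 schedule two 24-hour recalls during the run-in and two in the last two weeks of meals. Section 4.1 says of the recall software that "NDSR data output provides a series of files to allow nutrient analysis per ingredient, food, meal, and day". Section 6.2.1 names Fisher's exact test for dichotomous outcomes and t tests for timed variables. It adds a Stage 2 adjustment for pairing, with a paired t test as the only example. No analysis of continuous intake is named.

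Section 4.3.2 also gives every subject, in addition to the meals, a supply "with a daytime and nighttime protein supplement (approx. 15g protein) to be consumed daily at home during the same study days as MTM". Nothing removes that protein from the goal count.

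**The concern.** Whether the meals raise protein and energy intake is the first link in the trial's rationale. Two separate features weaken the planned answer.

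- **Scale.** Reducing four days of continuous data to a yes/no result discards information, and the sample is small: "We will enroll at least 20 subjects with a history of" HE of grade 2 or worse. The cut-points equal the nutritional targets of the meals in section 4.3.2, so a subject who eats the meals is expected to lie close to the line. A goal count also yields neither a mean change nor its SD, which the next trial would need. Section 1.1.3 gives that trial as the purpose: "The exploratory aims of this trial include measuring clinical changes for possible inclusion in the future trial".
- **Source.** The aim asks about the meals, but protein from bars, powder or liquid counts equally towards the goal.

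The conflicting wording and rank in sections 1.1.3 and 4.3.3 add a third problem: the reported intake outcome could be chosen after the data are seen.

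**Working it through.** **No stated figure to reproduce.** The plan gives no power, SD or effect size for intake. Section 6.1 states: "The sample size for this feasibility study not driven by any hypothesis test but reflects clinical judgement". From the documents come n = 20, the cut-point of 1.0 g/kg/day, two recall days per period and the supplement contents. All means, SDs and gains below are assumptions, as is the two-sided 0.05 level.

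**1. Goal count against paired mean change (protein)**

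Model: baseline mean 0.8 g/kg/day, between-person SD 0.2, day-to-day SD s = 0.2, 0.3 or 0.4, SD of individual gain 0.15. Each period is the mean of two days.

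- SD of the paired change = √(0.15² + 2·s²/2) = √(0.0225 + s²) = 0.25, 0.34, 0.43.
- SD of baseline intake = √(0.2² + s²/2) = 0.24, 0.29, 0.35, so 21%, 25% and 28% are at goal before the meals. With a gain of 0.20 the mean is 1.0 and 50% are at goal.
- Tests: paired t on the change; exact McNemar on goal met or not.

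| True gain (g/kg/day) | Goal count, power at s = 0.2 / 0.3 / 0.4 | Paired mean change, power |
|---|---|---|
| 0.20 | 47% / 31% / 20% | 93% / 72% / 50% |
| 0.30 | 85% / 66% / 46% | 100% / 97% / 84% |
| 0.36 | 95% / 82% / 63% | 100% / 100% / 94% |
| 0.47 | 100% / 97% / 87% | about 100% |

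These are simulated values. A direct calculation (noncentral t, and exact McNemar with bivariate normal cell probabilities) agrees within about one percentage point.

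A second parameterisation (SD 0.3 in each period, within-person correlation 0.5, baseline mean 0.7 to 0.9) gives, for gains of 0.15, 0.20 and 0.30:

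- paired t: 57%, 81%, 99%
- exact McNemar: 10–18%, 22–33%, 61–69%
- unpaired Fisher, the test section 6.2.1 names before its pairing adjustment: 9–11%, 18–23%, 54–58%

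McNemar would need about 46 to 63 subjects to match the paired t at 20.

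**2. What the supplements contribute (protein)**

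- Bar 10–17 g plus night supplement 15–16 g: 10 + 15 = 25 g to 17 + 16 = 33 g a day; nominally 2 × 15 = 30 g.
- Per kg at 70 kg: 25/70 = 0.36 to 33/70 = 0.47 g/kg.
- Other food needed to reach 1 g/kg with 30 g of supplement and no delivered meal: 1 − 30/70 = 0.57 (70 kg); 1 − 30/80 = 0.63 (80 kg); 1 − 30/100 = 0.70 (100 kg).
- Supplements alone: even 33 g at 50 kg is 0.66 g/kg, below the goal.
- With baseline mean 0.7–0.9 and SD 0.25–0.35 at 70–90 kg, adding 30 g a day and changing nothing else moves the share at goal from 12–39% to 54–91%. Example: mean 0.8, SD 0.3, 80 kg gives P(Z > 0.67) = 25% before, and P(Z > −0.58) = 72% after adding 0.375.

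**3. Energy**

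At 4 kcal/g, 30 g of protein is 120 kcal, or 120/2400 = 5% of the 30 kcal/kg goal at 80 kg. The documents do not give the supplements' total energy. An assumed 300–500 kcal would be 12.5–21%. The supplement argument is therefore not shown for the energy goal.

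**4. The improvement wording in section 4.3.3**

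Under no change, the proportion improved is 50% if any rise counts. If it means newly reaching the goal, it is about 10–16%, half of the 19–32% who switch category. Without a definition the figure cannot be read.

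**The case against.** The aim is exploratory, the sample size rests on no hypothesis test and no power is claimed. Reaching a nutritional target is a legitimate, readable result, and the Significance section cites a guideline protein recommendation of roughly 1 g/kg actual body weight, so the cut-point is not only the meal specification. All this stands, and it is why goal attainment should remain as a descriptive line. It does not explain why the mean change is left out.

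Four stronger readings are tempting, and the documents do not support them.

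- *The goal count loses most of its power.* That depends on the gain. At 0.20 g/kg/day it keeps roughly 40–51% of the paired-t power (20/50 to 47/93). At 0.30 it keeps 55–85% (46/84 to 85/100), and more beyond that. The supplements alone could supply 0.36–0.47 g/kg at 70 kg if they do not displace other protein, so a large gain is plausible.
- *The supplements can satisfy the goal by themselves.* They close a gap in protein but do not reach 1 g/kg. If the two goals must be met jointly, energy may still block success.
- *A rise in intake cannot be credited to the meals at all.* The goal count does not isolate them, but the per-food recall output can separate the sources. The plan may also mean the whole package: the adherence definition in section 1.1.1 includes the evening snack, though it does not name the daytime bar.
- *Category switching creates a false signal.* Under no change, switching is symmetric, the share at goal is equal before and after, and exact McNemar rejects in only about 1% of trials. It is noise rather than bias.

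**Conclusion.** The point holds as two separate improvements to an exploratory analysis, plus one inconsistency to resolve.

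- The goal count is less sensitive than the paired mean change at n = 20: about 20–47% against 50–93% power for a 0.20 g/kg/day gain, and 46–85% against 84–100% for 0.30, narrowing for larger gains. The direction is secure; the sizes rest on assumed means and SDs. Whatever those are, a goal count supplies no mean change or SD for planning the next trial.
- For protein, 25–33 g a day of supplement counts towards the goal. A subject whose other food already gives about 0.57–0.70 g/kg (70–100 kg) can reach it without a delivered meal. This is not shown for energy.
- Sections 1.1.3 and 4.3.3 disagree on the definition and rank of the outcome.

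The loss of sensitivity comes from dichotomising and the attribution problem from the supplements; neither causes the other. None of this touches the primary outcomes of retention and adherence.

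**What to change.** - Make the main intake result the paired mean change in protein (g/kg/day) and energy (kcal/kg/day), averaging the two recalls in each period, with 95% CI and the SD of the change.
- Base it on the recalls. By section 4.1 the food frequency questionnaire covers the previous 90 days, so one completed near study day 81 looks back to before enrolment (81 − 90 = −9). It is also not described as separating sources.
- Keep the proportion meeting each goal as a descriptive line. State whether the goals are joint or separate and, if a test is reported, use a paired one.
- Reconcile sections 1.1.3 and 4.3.3 to one definition and one rank, and align section 1.2.
- Tabulate recall protein and energy by source: delivered meals, study supplements, other food.
- State that the uncontrolled pre-post design and the concurrent nutrition handout still limit attribution to the meals, whatever the scale.

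The cost is analysis wording and one extra table from data already to be collected. No visit, assessment or subject is added.

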3.2 EXCLUSION CRITERIA

The following exclusion criteria applies to all subjects in both stages.

1. Non-English speaking
2. MELD Score > 20
3. Pregnancy (self-reported)
4. Unable or unwilling to provide consent
5. History of liver transplant
6. Current or planned admission to a nursing facility
7. Serum creatinine ≥ 2.0 mg/dL (with the exception that we will include patients with a serum creatinine ≥ 2.0 mg/dL if they are receiving hemodialysis)
8. Disorientation at the time of enrollment
9. Barcelona-Clinic Liver Cancer (BCLC) Stage D Hepatocellular Carcinoma with Child-Turcotte Pugh (CTP) Class C
10. History of eating disorder

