4. STUDY INTERVENTIONS AND PROCEDURES

4.1 ASSESSMENTS

The following assessments will be completed at various time points with subjects in Stage 1 and Stage 2:

1. Demographics Questionnaire (DQ) (Appendix A)

Records will be reviewed and/or the participants will be asked to provide the following demographic information:

1. Sex
2. Age
3. Date of birth
4. Ethnicity
5. Race
6. Highest education level attained
7. Marital status
8. Occupation status
9. Income
10. Geographic description of residence

2. Short Form-8 Health Survey (SF-8) (Appendix B)

The SF-8 is an abbreviated version of an original 36-item health survey (SF-36). It is a generic multipurpose quality of life instrument. It contains psychometrically based physical and mental health summary measures. The eight domains include general health, physical functioning, role physical, bodily pain, vitality, social functioning, mental health and role emotional.

3. PROMIS Short Form 4a (General Self-Efficacy) (PROMIS SE) (Appendix C)

The PROMIS Self-Efficacy is a 4-item questionnaire to assess the patient's self-reported current level of confidence in managing chronic conditions.

4. EncephalApp – Stroop Test

A computerized, timed test of attention conducted on an iPad or smart device via a phone application that asks patients to identify the color of words. The score is the sum of the time it takes to complete color-word concordance and color-word discordance. A score of < 190 is considered 'normal' cognitive function. Subjects who are color-blind will be excluded from performing this test.

5. Liver Frailty Index (LFI)

The LFI is composed of 3-performance based tests and is a tool specifically developed in patients with cirrhosis to objectively measure physical function. The 3 tests are:

1. 30-sec Chair Stands: A functional analogue of lower extremity strength and a commonly used test, it is the number of rises from a seated to standing position in 30 seconds.
2. Hand grip Strength: The average of three trials, measured in the subject's dominant hand using a hand dynamometer.
3. Balance Test: The number of seconds that the subject can balance in three positions (feet placed side-to-side, semitandem, and tandem) for a maximum of 10 seconds each.

6. Animal Naming Test (ANT)

The animal naming test is a timed test that consists of subjects listing as many unique animals as possible in 60 seconds. This is a validated test used for the assessment of hepatic encephalopathy.

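### Normalization of individual Stroop and ANT scores is measured by overall proportions normal, which cannot show how many subjects normalized; handling of missing follow-up scores is unspecified

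*Combined protocol and SAP*

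**What the plan says.** Section 1.1.3 (Exploratory Aims), item 2, states for the Stroop: "We aim to evaluate whether there is normalization in individual scores, by comparing the proportion of subjects with a 'normal' score at baseline", compared with 11±2 weeks, "with a score of < 190 seconds defined as normal". Section 4.1 repeats the cut-off: "A score of < 190 is considered 'normal' cognitive function". For the ANT the wording is "We aim to evaluate whether there is normalization in scores, by comparing the proportion of subjects with a 'normal' score at baseline", compared with 11±2 and 24±3 weeks, "with a score of >10 animals defined as normal"; here the word for individual is absent. Both bullets also plan a comparison of the scores themselves.

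Stage 2 entry (Section 3.1) asks for an episode of HE of grade 2 or worse in the 180 days before enrollment. It does not ask for an abnormal Stroop or ANT. Section 3.2 excludes "Disorientation at the time of enrollment". No analysis set limited to subjects abnormal at baseline is defined.

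Section 6.2.1 names Fisher's exact test for dichotomous outcomes, then says that Stage 2 testing will be adapted to paired values; its only example is a paired t test. On size, Section 2 says "We will enroll at least 20 subjects" for Stage 2, and Section 6.1 says "The sample size for this feasibility study not driven by any hypothesis test but reflects clinical judgement".

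On missing scores, Section 4.1 withholds the Stroop from color-blind subjects, and Section 4.3.3 omits it at remote visits. Section 4.5 lets a visit that coincides with a hospital stay be rescheduled at the investigator's discretion. Section 4.4 covers death only for its date, cause and utilization data. No section says how a subject without a follow-up score enters the proportion.

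**The concern.** The aim concerns what happens to individuals; the measure is a comparison of two group proportions. A subject already normal at baseline counts in the proportion but cannot normalize. A subject who becomes normal is offset by one who becomes abnormal. The result therefore does not answer the question in the aim, most clearly for the Stroop, where individual scores are named. Item 3 of the same section does use a within-subject definition for quality of life (at least 5% improvement in SF-8), so cognition is handled differently from its neighbour without a stated reason.

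The second gap is the denominator. In a population chosen for recent overt HE, some missing follow-up scores will probably arise from HE, admission or death, and such missingness is informative. At stake is how the pilot's cognitive results are read when tests are considered for possible inclusion in the future trial.

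**Working it through.** The documents give no expected proportion, effect size or power for the Stroop or ANT, so there is no planned figure to reproduce. The only input from the documents is n = 20, the Stage 2 minimum. Every count below is an assumption for illustration.

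**1. What the planned measure estimates.** Cross-classify n subjects with scores at both visits: a normal at both, b abnormal then normal (gain), c normal then abnormal (loss), d abnormal at both.

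- Change in proportion normal = (a + b)/n − (a + c)/n = (b − c)/n.
- Normalization rate = b/(b + d).
- Worsening rate = c/(a + c).

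The first does not determine the second.

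**2. Same change, different individual results.** With 10 of 20 normal at baseline:

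| Normal at follow-up | Gains b | Losses c | Change | Normalized (exact 95% CI) | Exact McNemar p | Fisher p |
|---|---|---|---|---|---|---|
| 10/20 | 0 | 0 | 0 | 0/10 (0–31%) | 1.0 | 1.0 |
| 10/20 | 2 | 2 | 0 | 2/10 (3–56%) | 1.0 | 1.0 |
| 10/20 | 4 | 4 | 0 | 4/10 (12–74%) | 1.0 | 1.0 |
| 13/20 | 3 | 0 | +15 points | 3/10 (7–65%) | 0.25 | 0.52 |
| 13/20 | 5 | 2 | +15 points | 5/10 (19–81%) | 0.45 | 0.52 |
| 13/20 | 7 | 4 | +15 points | 7/10 (35–93%) | 0.55 | 0.52 |

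With 8/20 normal at both visits, 0 to 4 losses fit 0/12 to 4/12 normalized; with 12/20, they fit 0/8 to 4/8. Exact McNemar is the natural paired test here, but it weighs gains against losses, so pairing corrects the test and not the quantity estimated.

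**3. Subjects already normal.** If a share q is normal at baseline and 30% of the rest normalize with no losses, the overall rise is 0.3 × (1 − q): 21, 15 or 9 points for q = 0.3, 0.5 or 0.7.

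**4. No follow-up score.** Suppose nobody's status changes, 10/20 are normal at baseline, and m of the abnormal subjects are not tested.

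- Unpaired, untested dropped: 10/(20 − m) at follow-up, against 10/20 = 50%. For m = 1, 2, 4, 5 this is 52.6%, 55.6%, 62.5%, 66.7%, an artificial rise of 2.6 to 16.7 points (2.1 to 13.3 if 8/20 are normal at baseline; 3.2 to 20.0 if 12/20).
- Paired completers, m = 4: 10/16 = 62.5% at both visits. The rise disappears, but the four subjects are still omitted.
- Untested counted as not normal: 10/20 = 50% at both visits.

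**The case against.** The broader aim in item 2 is whether meals improve cognitive function. If gains equal losses, no net change is the right group-level answer, so the overall proportion is a legitimate summary. That stands, and it is why the proportion should stay. Score comparisons are already planned, and deaths, transplants and admissions for overt HE are reported separately under item 5, so severe outcomes are not lost to the study.

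A headline rate among subjects selected for an abnormal baseline would also be more exposed to regression to the mean, because Stage 2 has no control arm. That stands too, and it argues against replacing the overall proportion.

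Three stronger readings are tempting, and the documents do not support them:

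- A reader might infer that the plan leaves out subjects too encephalopathic to be tested. No section says so; the plan is silent. It also has features that limit missing scores: a follow-up window of study days 66–96, the ANT by phone at 24±3 weeks, rescheduling after discharge, and a request for early final assessments on discontinuation (Section 4.6).
- A reader might infer that the planned analysis would show improvement when nobody improved. That needs an unpaired comparison. Section 6.2.1 promises pairing in Stage 2, and a paired completer comparison shows no such rise.
- A reader might infer that these results decide the endpoint of the definitive trial. Section 1.1.3 speaks only of possible inclusion, and no threshold is set.

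**Conclusion.** The mismatch between aim and measure holds. The planned comparison yields the net change only and cannot show how many individuals normalized, with or without paired testing. In the illustration, a net change of zero fits 0% to 40% normalization among subjects abnormal at baseline, and a rise of 15 points fits 30% to 70%. The size depends on how many subjects are normal at baseline and how many worsen, neither of which the documents give. The case is clearest for the Stroop and weaker for the ANT.

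The handling of missing follow-up scores is unspecified, not wrongly specified. Its effect depends on whether the comparison is unpaired (artificial rise) or paired among completers (no rise, but subjects omitted).

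The importance is minor. Section 1.1.3 classes the aim as exploratory, although Sections 1.2 and 4.3.3 list the same tests among secondary outcomes. The primary outcomes are retention and adherence, the sample size rests on no hypothesis test, and the results inform the choice of a later endpoint without deciding it.

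**What to change.** In Section 1.1.3, item 2, keep the overall proportions and the score comparison, and add for each test and follow-up visit:

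- the baseline-by-follow-up 2x2 table;
- normalized / abnormal at baseline and worsened / normal at baseline, each with an exact 95% confidence interval;
- a statement that the two rates are read together, because without a control arm regression to the mean will produce some normalization among subjects abnormal at baseline;
- the number without a follow-up score, by reason;
- a sensitivity analysis that counts subjects who died, or could not be tested because of HE or admission, as not normal at that visit;
- transplanted subjects shown separately;
- color-blind subjects and remote visits treated as not applicable for the Stroop.

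The cost is wording and one table per test and visit, from data already collected. The rates have smaller denominators and wider intervals than the overall proportion; for example, 4/10 has an interval of 12% to 74%. The sensitivity analysis mixes cognition with death and admission, so it should be labelled a composite and kept beside the main result.
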